## **Project Narrative**

### **Background and Significance**

Tracheal intubation is one of the most important interventions in the stabilization of critically ill or injured children. Advanced airway skills training is one of the major pillars of the ACGME pediatric program requirements for resident and fellowship education (Accreditation Council for Graduate Medical Education, 2007). The pediatric airway presents unique anatomic challenges depending on the patient age, size and underlying condition. These challenges, coupled with low frequency of pediatric trainee exposure to advanced airway management, make tracheal intubation procedural competency difficult to achieve. As a result, tracheal intubation in infants and children is associated with high levels of operator stress as well as patient morbidity and mortality.

The ability to manage the pediatric airway, which includes anticipating potential difficulties and choosing an appropriate approach, remains one of the most vital skills to develop when caring for critically ill children. Provider training level has been found to correlate with patient outcome during advanced airway management in selected environments including the operating room, delivery room and Neonatal Intensive Care Unit (NICU). Pediatric trauma patients intubated by less experienced emergency medical personnel in the field have increased morbidity and mortality when compared to similar patients intubated by pediatric-trained hospital personnel. A limited number of studies from neonatal resuscitation demonstrated that resident trainee success rates are moderate at best, with 1/3 of upper level pediatric residents unable to intubate a very low birth weight (<1500 grams) neonate. The RRC agreed that neonatal intubation is a critical skill, but respondents to a survey sent to Residency Program Directors determined that "many residents do not develop competence in that area" and that a "more robust and standardized method is needed for teaching procedural skills and for documenting

Version #3

Date: September 19, 2017

pg. 2

competence". A survey of pediatric emergency room directors found that the number of intubations necessary to maintain skill in this area was inadequate. Even more concerning is that procedural skills such as intubation deteriorate rapidly over time (within the first year).

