### **Hypothesis and/or Specific Aims or Objectives**

Specific Aim 1. *Assess the impact of this educational manikin intervention on live patients.*

We hypothesize learners in the Intervention Group vs. the Control Group will have enhanced success in intubation as determined by the number of attempts and time required for intubation of live patients.

Specific Aim 2. *Assess the satisfaction of this educational intervention and equipment.*

We hypothesize pediatric residents will have increased satisfaction scores and confidence for intubating live patients in the Intervention Group vs. the Control Group.

Specific Aim 3. *Assess the association of confidence in intubation with actual success in intubation.*

We hypothesize increased confidence will be associated with increased intubation success.

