## **Methods**

This research study will include 95 resident physicians. We anticipate 80 residents will enroll, similar to our previous study in which 82 residents participated. Residents will be randomized to the Intervention Group or the Control Group. This study will be explained to potential participants as they begin their assigned rotation to the Neonatal Intensive Care Unit (NICU). The explanation of the study and the Information Sheet will be introduced during the first five (5) days of this rotation. Residents will be allowed to ask any questions they feel necessary and take as much time as needed in order to make a fully informed voluntary consent. It will be explained that their participation in this study is completely voluntary and a decision to not participate will have no impact on their training or standing in the residency program. Randomization will occur by the month the resident is assigned to the NICU.

All participants will:

- Receive NRP training and certification offered at the beginning of their residency
- Complete a Baseline Survey
- Complete a Baseline Cognitive and Simulation Assessment
- Have a Stabilization Room video recording as part of the quality improvement process for neonatal resuscitation
- Complete a Cognitive and Simulation Assessment at the end of the month
- Complete an End of Rotation Survey

Residents who are randomized to the Intervention Group will, in addition:

- Observe a 7 minute NRP video
- Complete a hands-on intubation simulation with [name] instructing:
  - Using state of the art technology, a Storz C-MAC video laryngoscope
  - Identifying anatomical landmarks
  - Practice on the manikin until intubation occurs within 15 seconds

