## **Evaluation Plan**

Using data from our previous intubation study using a manikin, we estimate a sample size for this study is 27 residents in each group. We recruited more than that for the manikin study, and for that study residents were required to come back for a post test. Thus, we anticipate no major difficulties in recruitment.

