Study Title: *“Manikin To Patient Intubation: Does It Translate?”*

Principal Investigator: R. [name].
University of Arkansas for Medical Sciences
[name]
[name]
[contact]
Email: [contact]

Study Location: University of Arkansas for Medical Sciences
[name]
[name]

Date: September 19, 2017

NCT number: NCT03046966

Statistical Analysis

Chi-square tests with the Benjamani-Holm p-value correction to account for test multiplicity will be used to analyze the difference in baseline measures and demographics. Chi-square testing will be utilized for comparing end of survey comfort. Logistic regression will be utilized to compare overall and first-time intubation success rates between the control and intervention groups. Logistic regression will be used to compare the difference in success rate between training level groups. To account for over-dispersion, a negative binomial regression will be utilized to assess difference in overall and first-time intubation success counts.

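### As written, the SAP's training-level logistic regression has no arm term, so it averages the level gap over both arms; adding arm and reporting level by arm descriptively would improve this secondary analysis at little cost

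*SAP*

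**What the plan says.** The SAP's Statistical Analysis section gives two separate logistic regressions. The first is by arm: "Logistic regression will be utilized to compare overall and first-time intubation success rates between the control and intervention groups". The second is by training level: "Logistic regression will be used to compare the difference in success rate between training level groups". The second sentence names no arm term, interaction, stratum or restriction to controls. It does not define the levels or say whether the outcome is overall or first-attempt success. A further sentence says that "a negative binomial regression will be utilized to assess difference in overall and first-time intubation success counts", without naming the grouping factor. Nothing else in the SAP or protocol fills these gaps.

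On allocation, the protocol's Methods state: "Randomization will occur by the month the resident is assigned to the NICU". No stratification by training level is described. All residents receive NRP training. Only the intervention group gets the study's hands-on session before live intubations are recorded, and controls are offered it when the rotation ends. The live data therefore come from a mixture of study-trained and control residents.

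Aim 1 is an arm contrast: "learners in the Intervention Group vs. the Control Group will have enhanced success in intubation". None of the three aims concerns training level.

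**The concern.** A level comparison that ignores arm can go wrong in two ways.

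- **Confounding by arm.** If a larger share of one level falls in intervention months, the level difference picks up part of the training effect. Month-based allocation without stratification leaves this to the rota.
- **Averaging over unlike gaps.** If training helps one level more than another, the level gap differs between arms. The pooled figure lies between the two arm-specific gaps, and a model without an arm-by-level term cannot show at which level training helps.

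A reader of the results would probably want either the level gap under usual training (controls) or the training effect within each level. A level-only model isolates neither. At stake is the interpretation of one planned secondary result.

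**Working it through.** **The plan's own figure.** The only design figure is in the protocol's Evaluation Plan: "we estimate a sample size for this study is 27 residents in each group". Its alpha, power, effect and variance are not stated, so it cannot be reproduced. At an assumed two-sided 5% level and 80% power it would imply a standardised difference of √(2/27) × (1.960 + 0.842) = 0.76. It does not concern the level comparison and is used below only to bound the cell sizes.

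**Inputs.** Enrolment is from Methods: "We anticipate 80 residents will enroll, similar to our previous study in which 82 residents participated". Everything else is assumed: two equal-sized levels (junior and senior), one binary outcome per resident, and control success of 40% (junior) and 60% (senior). The control level odds ratio (OR) is then (0.60/0.40)/(0.40/0.60) = 2.25.

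**Formula.** If a share f of a level is in the intervention arm, its pooled success is (1 − f) × control rate + f × trained rate. The pooled level OR is the ratio of the two pooled odds.

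**Step 1: balanced arms (f = 0.5), same training OR at both levels.** With a training OR of 2.25, the trained rates are 60.0% and 77.1%. The pooled rates are 50.0% and 68.6%, giving a pooled OR of 2.18. Training ORs of 1.5 and 4 give 2.23 and 2.08. The OR within each arm is 2.25, so the distortion is small.

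**Step 2: arm share differs by level, training OR 2.25 at both levels.** The OR within each arm is still 2.25.

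| Juniors in intervention arm | Seniors in intervention arm | Pooled junior | Pooled senior | Pooled OR |
|---|---|---|---|---|
| 40% | 60% | 48.0% | 70.3% | 2.56 |
| 60% | 40% | 52.0% | 66.9% | 1.86 |
| 30% | 70% | 46.0% | 72.0% | 3.02 |

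In this step, adding arm to the model recovers 2.25.

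**Step 3: balanced arms, training effect differs by level.**
- Juniors only (40% to 60%): the gap is 20 points in controls and 0 in trained residents. The pooled gap is 0.5 × 20 + 0.5 × 0 = 10 points. The ORs of 2.25 and 1.00 pool to 1.50.
- Seniors only (60% to 80%): the gaps of 20 and 40 points pool to 30. The ORs of 2.25 and 6.00 pool to 3.50.

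**Step 4: testing the level gap when there is truly none.** This is conditional on an assumed imbalance, a 25-point arm effect, 40 residents per level and a variance of 0.24. SE = √(2 × 0.24/40) = 0.110.
- Arm shares 20 points apart: bias = 0.20 × 25 = 5 points. Rejection = Φ(−1.96 + 0.456) + Φ(−1.96 − 0.456) = 7.4%.
- Arm shares 30 points apart: bias = 0.30 × 25 = 7.5 points. Rejection is 10.5% by the same formula.

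With no imbalance the rate stays at the nominal 5%.

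**Step 5: what the better model can deliver.** With 80 residents in four equal cells of 20, the 95% half-width of a within-level arm difference (or a within-arm level gap) is 1.96 × √(2 × 0.24/20) = 0.30, or 30 points. For the juniors-only 40% to 60% case, the interaction log OR is ln 2.25 = 0.811, with SE √(4/(20 × 0.24)) = 0.913. Power = Φ(0.811/0.913 − 1.96) = 14%. With 54 residents (13.5 per cell), the SE is 1.111 and power is 11%.

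**The case against.** The strongest case against has five parts.

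- **The sentence is ambiguous.** It follows directly after the arm comparison and could mean that the arm difference is compared across levels. That stands as a possible reading, so the SAP is under-specified rather than shown to exclude arm. It does not settle the matter, because that reading needs an arm-by-level term, which is not named either.
- **The harm is conditional.** A reader might infer that the pooled level gap describes neither arm. The documents do not support this: with balance and a common training OR it is close to both (Step 1). Imbalance and effect modification are possible but not shown, and every rate above is assumed.
- **The purpose of the training goal.** A reader might infer that the 15-second manikin goal is intended to even out junior and senior skill. The protocol presents it only as a training target, half the NRP time allowance. The Background figure, "1/3 of upper level pediatric residents unable to intubate a very low birth weight (<1500 grams) neonate", is an absolute failure rate and not a junior-senior gap, so it does not make the level gap central to the rationale.
- **No aim depends on training level.** This stands. A marginal level comparison is also a legitimate descriptive question if it is labelled as such.
- **The better model will not find where training works.** This stands as a limit on testing. It supports reporting estimates with intervals; it does not justify leaving arm out.

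**Conclusion.** The point holds as a low-cost improvement to a secondary analysis. On its plain reading, the training-level regression omits arm and averages over study-trained and control residents. The size of the problem depends on conditions the documents leave open. It is negligible with balanced arms and a common training OR (2.25 becomes 2.08 to 2.23). It is moderate if arm shares differ by level (1.86 to 3.02 under the assumed splits). If training helps only one level, the pooled figure is a blend (20 and 0 points become 10). The false-positive rates of 7.4% and 10.5% apply only under the assumed imbalances.

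A reader might go further and infer that the trial's main conclusion is compromised. It is not: the Aim 1 arm comparison is a separate model and is untouched. The figures rest on two equal levels, one outcome per resident and illustrative success rates. The SAP defines no levels, and residents may make several attempts, so actual precision could differ.

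**What to change.** Replace the training-level sentence in the SAP with text that:

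1. defines the training levels and names the outcomes (overall and first-attempt success);
2. specifies, for each outcome, a logistic model with training level and arm, giving an arm-adjusted level gap;
3. adds the arm-by-level term to report the level gap in each arm and the arm effect at each level, with 95% confidence intervals, labelled descriptive and not tested.

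At a minimum, add arm to the level model. That removes the confounding in Step 2 but not the averaging in Step 3.

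The cost is a sentence or two and no new data, since the SAP already plans to use training level and arm. The downside is imprecision. Intervals are about ±30 points with 20 residents per cell. With three levels (assumed), 80/6 gives about 13 per cell and 1.96 × √(2 × 0.24/13.3) = 0.37, or ±37 points. The report should therefore say that the absence of a visible difference between levels is not evidence that training works equally well at all of them.

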During the monthly rotation of each resident, ongoing data will be collected on the residents' ability to successfully intubate on the first attempt, the total number of attempts to intubate, and the total number of successful attempts at intubating a neonate within 30 seconds, the time limit set by NRP. All live intubations performed in the Stabilization Rooms will be recorded and reviewed by designated members of the NICU Safety Committee. The recorded videos of study participants will also be reviewed by [name] and [name], R.N. The information obtained from the video recordings will be kept in a safe, secure file that is password protected. At the end of the monthly rotation each resident, including those in the Control Group, will be offered the opportunity to complete the Hands-on Intubation training simulation with [name].

Angel Eye Cameras and control modules will be placed on the patient beds in the NICU Resuscitation Rooms which will be used for recording and monitoring infant intubation procedures. The cameras will be placed on the bed above the infant and staff while the control panel will be on a nearby wall to allow for easy starting and stopping of recording and monitoring of recording during the procedure. The control panel will have access to start/stop

[figure not shown]

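### The count model for intubation success has no stated denominator and is not ranked against the logistic model on rates, so procedure volume can make the two disagree

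*SAP*

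**What the plan says.** The SAP (Statistical Analysis) plans two models for the same pair of outcomes, overall success and first-time success.

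- On rates: "Logistic regression will be utilized to compare overall and first-time intubation success rates between the control and intervention groups".
- On counts: "To account for over-dispersion, a negative binomial regression will be utilized to assess difference in overall and first-time intubation success counts".

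The second sentence mentions no offset, exposure or denominator. Neither model is called primary or supportive, and nothing says what happens if they differ. The protocol names no primary analysis either.

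Three features of the protocol bear on this.

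- Allocation (Methods): "Randomization will occur by the month the resident is assigned to the NICU". The Abstract describes alternating months.
- Data collected (Methods): "ability to successfully intubate on the first attempt, the total number of attempts to intubate, and the total number of successful attempts", the last of these tied to a 30-second limit. No passage fixes or sets a minimum number of live intubations per resident.
- Specific Aim 1 expects "enhanced success in intubation as determined by the number of attempts and time required for intubation of live patients", so the number of attempts is itself treated as something training may change.

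**The concern.** A success count without a denominator is the product of how often a resident intubated and how well. The first factor depends on deliveries and staffing in the month of rotation, and possibly on skill, since a better operator may need fewer attempts. Because whole months are allocated, a busy or quiet month moves all its residents in one arm together. Volume can therefore add noise to the count comparison or shift its ratio away from the skill ratio.

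Two models with different estimands then address the same outcomes without a ranking. If one result is significant and the other is not, the choice is made after the data are seen. The SAP also raises over-dispersion only for the count model, which could invite a preference for that result, although it is the one that does not isolate skill.

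**Working it through.** **Inputs.** From the protocol: 80 residents expected (Methods), 27 per group (Evaluation Plan), alternating months (Abstract). Assumed, because the documents give no values: 16 months of 5 residents; Poisson attempts with mean 4 per resident; resident skill SD 0.5 on the logit scale; log-normal monthly volume with coefficient of variation (CV) 0 to 0.6; and the success rates.

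**The plan's own figure.** The protocol says "we estimate a sample size for this study is 27 residents in each group" but gives no alpha, power, effect size or SD, so the figure cannot be reproduced. At two-sided 0.05 and 80% power it would fit a standardized difference of (1.96 + 0.84) × √(2/27) = 0.76. The present point does not depend on it.

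**Step 1: what the count model estimates.** Expected count = m × p (procedures × success probability). The count ratio is (m_I × p_I)/(m_C × p_C), for intervention (I) over control (C).

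- Success 50% in both arms, 2 (control) vs 3 (intervention) procedures: (3 × 0.5)/(2 × 0.5) = 1.5; odds ratio 1.0.
- Success 40% vs 60%, 3 vs 2 procedures: (2 × 0.6)/(3 × 0.4) = 1.0; odds ratio (0.6/0.4)/(0.4/0.6) = 2.25. With procedures as offset, the ratio would be 0.6/0.4 = 1.50.

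These volumes show the mechanism; they are not a forecast.

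**Step 2: how often the planned analyses disagree.** Success 0.40 vs 0.60, 1000 simulated trials per row. The first four result columns are power.

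| Monthly volume CV | Raw-count negative binomial | With log(attempts) offset | Planned logistic | Month-clustered logistic | Raw count and planned logistic disagree at 0.05 |
|---|---|---|---|---|---|
| 0 | 65% | 75% | 92–93% | 85% | 29% |
| 0.2 | 64% | 76% | 92–93% | 86% | 32% |
| 0.4 | 57% | 76% | 92–93% | 85% | 37% |
| 0.6 | 50% | 76% | 92–93% | 87% | 47% |

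Repeat simulations on the same inputs gave 27–29% at CV 0, 39–44% at CV 0.4 and 40–49% at CV 0.6. A fair summary is about 29%, rising to 40–47%. The power gaps (92 − 65 = 27 points at CV 0; 92 − 50 = 42 at CV 0.6) account for nearly all of the disagreement, so it is almost always the count model that misses the difference.

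With 27 per arm, power at CV 0 / 0.4 is 48 / 44% for raw counts, 55 / 52% with the offset and 66 / 66% for the month-clustered logistic.

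**Step 3: how much of this is volume.** With exactly 4 attempts for every resident, the two planned analyses still disagree in 16% of trials (power 79% vs 94–95%). With Poisson attempts at CV 0, the same simulation gave 27%, so random volume adds 27 − 16 = 11 points. At CV 0.4 it gave 39–44%, so volume adds 23–28 points. The offset column agrees: adding a denominator still leaves a power gap of 92 − 76 = 16 to 93 − 75 = 18 points. That remainder comes from fitting a count model to a binomial outcome and from a logistic model that ignores clustering.

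**Step 4: other success rates.** At 0.20 vs 0.40, disagreement is about 8% at CV 0 and 23% at CV 0.4. At 0.40 vs 0.50 with CV 0 it is 28%, of which 24 points remain when volume is fixed.

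**Step 5: a conditional case.** Suppose attempts on an infant stop at success, with at most 3 (assumed).

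- Overall success per infant: 1 − 0.6³ = 0.784 vs 1 − 0.4³ = 0.936, a ratio of 1.19.
- Attempts per infant: 1 + 0.6 + 0.36 = 1.96 vs 1 + 0.4 + 0.16 = 1.56, a ratio of 0.80.
- Success per attempt keeps its ratio of 1.50.

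Raw-count power for overall success is then 20–30%, and the planned analyses disagree in 64–74% of trials.

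**The case against.** The strongest reply is that the planned logistic regression already compares rates. That stands: the trial has an analysis of success per procedure, and only the second analysis is affected.

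It can also be said that the SAP does not exclude an offset, and that the protocol collects "the total number of attempts to intubate". Both are true. But the SAP sets counts beside rates, and nothing links the collected attempts to the count model. Attempts and infants are different possible denominators, so an offset left unstated would still be ambiguous.

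On size, the reply is largely right. A reader might infer that all of the disagreement is due to volume, or that 29–47% is the full range. Steps 3 and 4 show neither is so. Three other inferences go beyond the documents:

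- **That the analyses would disagree in two thirds of trials or more.** The 64–74% needs attempts to stop at success, which no passage states. If success means within 30 seconds, a slower placement could end the attempts without counting as a success, and step 5 does not model that.
- **That the count model would produce many false positives.** Rejection rates of 30–79% with no skill difference appear only when unequal volumes such as 2.4 vs 3.6 or 2 vs 4 procedures are imposed between arms. No passage supports a sustained imbalance of that kind, and alternating months work against one. With equal volume and no effect, rejection was 4.5% for the count model and 4.2% for the logistic.
- **That both models analyse Aim 1 as worded.** The aim is stated in terms of attempts and time, and neither model takes these as its outcome.

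Finally, handling allocation by month is partly a separate matter. It belongs here only because the SAP seeks to deal with over-dispersion through the count model, and the rate model is the better place for it.

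**Conclusion.** The concern holds in a limited form. The SAP leaves the count model without a denominator and does not rank it against the rate model. With volume not fixed and allocation by month, the count model as written mixes procedure volume with skill. This follows from the text and simple arithmetic, and is firm.

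The size is illustrative and rests on the assumed rates, volumes and skill spread. Disagreement could be under 10% of trials or above 40%, and some of it would remain with identical volumes. The main harm is a second analysis that often misses a real difference, with no rule for which result to report. It should be fixed, but it does not invalidate the planned comparison of rates.

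**What to change.** Change the SAP wording as follows.

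- Make the rate analysis the main analysis of intubation success: logistic regression of successes out of recorded attempts. For first-time success use first attempts, once the sponsor confirms that this means the first attempt on each infant.
- Handle over-dispersion and allocation by month in that model, by month-clustered standard errors with a t reference on (months − 2) degrees of freedom, or by random intercepts for month and resident.
- Drop the count model, or keep it as supportive with a log(attempts) offset, or log(first attempts) for first-time success. Note that the offset model is conservative if success does not vary by month: it rejected in 1.2–1.7% of simulated trials with equal skill.
- Report attempts per resident, and the number of residents with no live intubation, by arm.

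**Cost.** Total attempts are already collected. First attempts would have to be tabulated from the reviewed recordings, which should be available: "All live intubations performed in the Stabilization Rooms will be recorded and reviewed by designated members of the NICU Safety Committee". Month clustering costs about 5–9 points of power against the planned logistic at mean 4 attempts and 80 residents. Part of that is the price of correct error control, since the unclustered model rejected in 7–9% of trials with equal skill and the clustered one in 4.3–6.5%. Residents with no live intubation leave the analysis. At an assumed mean of 4 attempts that is 2–7% of residents, or 10–18% if attempts cluster on infants; at a mean of 2 it is 14–17% or 32–35%.

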## **Study Population**

### Inclusion Criteria

Male and female residents from 18-89 years of age who have been assigned to the NICU for a monthly rotation are eligible to participate. At the beginning of all NICU rotations, all pediatric residents will be invited to participate in this research.

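### The negative binomial model compares raw success counts with no denominator, so it mixes how often residents intubated with how well; make the per-attempt logistic model decide Aim 1 and give any count model an offset

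*SAP*

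**What the plan says.** The SAP plans two analyses of the same live outcomes. The first concerns rates: "Logistic regression will be utilized to compare overall and first-time intubation success rates between the control and intervention groups". The second concerns counts: "To account for over-dispersion, a negative binomial regression will be utilized to assess difference in overall and first-time intubation success counts". For neither does it name the unit of analysis, the set of residents or the handling of repeated attempts by one resident. It names no offset for the counts and does not say which model decides Aim 1.

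The denominator exists. Protocol Methods lists, among the data collected in each rotation, first-attempt success, "the total number of attempts to intubate" and the successes within the 30-second limit. Aim 1 itself names the number of attempts, with time, as a measure of success.

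No text says what happens to a resident who performs no live intubation. The nearest is the Methods item giving every participant a Stabilization Room video recording. It does not promise that the recording shows that resident intubating. The only exclusion is unwillingness to take part.

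On assignment, Methods says: "Randomization will occur by the month the resident is assigned to the NICU".

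**The concern.** A success count is the number of attempts multiplied by the chance of success at each. Aim 1 asks whether training improves the second factor. A count without a denominator responds to both, so it can differ between groups because one group had more infants to intubate. It can also fail to differ when skill does, because attempts moved the other way.

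A quiet or busy month changes the opportunities of every resident assigned to it, and all of them are in the same group. Chance imbalance in exposure is therefore more likely than if residents had been assigned one by one.

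The two models may also rest on different residents. With no rule saying which decides Aim 1, they could disagree and the plan would not say how to read the result.

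**Working it through.** **Inputs.** The documents give no attempts per resident, no per-attempt success rate and no share of residents with no live intubation. The plan therefore has no figure of its own on this point to reproduce. Methods anticipates 80 residents ("We anticipate 80 residents will enroll, similar to our previous study in which 82 residents participated"), so I take 40 per group, assuming an even split. Also assumed: mean attempts of 1 to 3 per resident, dispersion of attempts 0 (Poisson) or 1, correlation of success within resident (ICC) 0.1 to 0.3, and a per-attempt success of 66.7%. The one-third failure figure in the Abstract and Background is per resident, for very low birth weight neonates, so it does not establish that last value.

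**1. What each model does with a resident (illustration).**

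| Resident | Rate | Count |
|---|---|---|
| No live intubation | 0/0, undefined | 0 |
| Three attempts, none successful | 0/3 = 0 | 0 |

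The rate separates the two residents; the count does not. Residents of the first kind need not be rare. The share with none is exp(-m) under Poisson, or 1/(1+m) at dispersion 1. For m = 1, 2, 3 this gives 36.8%, 13.5%, 5.0% and 50.0%, 33.3%, 25.0%.

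**2. Equal skill, unequal exposure.** Expected count = mean attempts x success probability: 2.0 x 0.667 = 1.33 v 1.5 x 0.667 = 1.00. The rate ratio is 0.75, while the per-attempt odds ratio is 1.

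**3. How often that is declared a difference.** For the count model, SE = sqrt[(1/mu0 + d)/40 + (1/mu1 + d)/40], where d is the dispersion, and the effect is ln(0.75) = -0.288.
- d = 0: SE = sqrt[(0.75 + 1.00)/40] = 0.209, z = 1.38, rejection about 28%.
- d = 1: SE = sqrt[(1.75 + 2.00)/40] = 0.306, z = 0.94, rejection about 16%.

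Simulation (2,000 to 3,000 trials per scenario, all 40 residents per group in the count model) gives 14.3-27.2%. With log(attempts) as offset, residents with at least one attempt and errors robust by resident, it gives 4.5-5.7%. Repeat simulations agree (count model up to about 28%, per-attempt analysis up to about 6%).

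**4. Exposure varying by month only.** With equal skill, mean 2 attempts, ICC 0.2, seven months per group and a between-month coefficient of variation in exposure of 0.2 to 0.5, the count model rejects in 7.1-18.8% of trials. A per-attempt logistic model with robust errors rejects in 5.2-6.6%. Skill and case mix did not vary by month in this check.

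**5. Equal exposure.** With no true difference, the count model rejects in about 4-7% of trials, so its level is sound. The cost is power. For 67% v 83%, Poisson attempts with mean 2 and ICC 0.1, it has 20.9%, against 58.6% with offset and robust errors. A per-attempt logistic model with robust errors has 60.1%, essentially the same as the offset model.

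**6. Clustering in the logistic model.** With equal skill, a per-attempt logistic model that ignores repeated attempts by one resident rejects in about 7-20% of trials over these settings. Robust errors are needed there too.

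**7. Attempts are partly an outcome.** Take 83.3% success with 1.6 attempts per resident v 66.7% with 2.0. Expected counts are 1.6 x 0.833 = 1.33 and 2.0 x 0.667 = 1.33, so the benefit vanishes from the count. The same pattern arises if every resident has 1.33 infants and tries until success: 1/0.833 = 1.2 and 1/0.667 = 1.5 attempts per infant, and 1.33 x 1.2 = 1.6, 1.33 x 1.5 = 2.0. Opportunity is then equal and skill alone drives the attempts.

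**The case against.** The strongest reply is that the SAP is one short paragraph. It does not say that every enrolled resident enters the count model, nor that an offset is excluded, and the investigators may intend one. That is fair: the fault lies in the model as literally written. Stating the intention costs a clause.

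Second, the imbalance is assumed. Nothing in the documents predicts 2.0 v 1.5 attempts, and with equal exposure the count model keeps its level. This stands. The inflated error is conditional, although assignment by month makes the condition credible.

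Third, Aim 1 makes the number of attempts an outcome, so treating attempts as pure exposure is wrong. This also stands, as step 7 shows. It is why success per infant and exposure by group belong beside the per-attempt result.

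Two stronger readings are tempting. A reader might infer that the plan as a whole is badly underpowered and that an offset rescues it. The documents do not support that: the SAP already plans logistic regression on rates, and run per attempt with robust errors it has the power that the offset would bring. A reader might also infer from "Using data from our previous intubation study using a manikin, we estimate a sample size for this study is 27 residents in each group", backed only by "we anticipate no major difficulties in recruitment", that the trial will have too few residents with a live outcome. The text leaves the meaning of 27 open, but enrolment is not capped there ("At the beginning of all NICU rotations, all pediatric residents will be invited to participate in this research"). With 40 per group, 27 remain unless more than 13 of 40 (32.5%) have no live intubation. A shortfall is possible but not shown.

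**Conclusion.** The concern holds for the count analysis. As literally written, that model confounds opportunity with skill, scores a resident with no live intubation as a failure, and may use different residents from the logistic model. Its false-positive rate is about 14-27% under an assumed 2.0 v 1.5 attempts with 40 per group, and near 5% when exposure is equal. In the second case the harm is lost power in this model only. All these sizes rest on the assumed attempts, success rate, dispersion and ICC. The structural fault does not: it follows from a count with no denominator. The SAP should be amended, because a better-specified analysis is available from data already collected. The point does not show that the trial is too small, or that exposure will in fact differ.

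**What to change.** In the SAP:

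1. Name two logistic models as the analyses that decide Aim 1: per attempt for overall success, and per infant on the first attempt for first-time success. Fit them in residents with at least one live intubation, with standard errors robust to clustering by resident. Add a sensitivity analysis clustered by rotation month, because assignment is by month.
2. If the negative binomial model is kept, label it supportive. Give it an offset (log attempts for overall success, log infants first attempted for first-time success), the same residents and robust errors. Each element is needed: dropping residents with no attempts but leaving out the offset still gives 10-13% false positives at 2.0 v 1.5 attempts, and an offset without robust errors is too conservative.
3. Report by group the number enrolled, the number with no live intubation, and the infants and attempts per resident. Show success per infant as well, since attempts arise after assignment and are themselves an Aim 1 outcome.

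The cost is a few sentences, with no extra residents, visits or data source: attempts are already collected and Stabilization Room intubations recorded. There are two downsides. Residents with no live intubation leave the models, a selection made after assignment, which is why their number must be shown by group. And the offset count model becomes nearly a duplicate of the logistic model, so dropping it would also be reasonable.
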